Enrollment is anticipated to take approximately 18 months. The study will enroll 480 patients from 12 active study sites, averaging 27 patients a month for a mean of 40 patients enrolled per site.

SITE COMMITMENT

Sites will be expected to:

- 1) Sign a site agreement with DCRI, which includes site payment benchmarks, specifying IRB fees and site payment information.
- 2) Obtain IRB Approval prior to enrolling any patients and maintain approval throughout the study.
- 3) Screen patients, and obtain informed consent and contact information from all patients, via the provided iPad
- 4) Have institution Wi-Fi access and ability to use the iPad to submit signed informed consent, patient contact information, and questionnaires to DCRI
- 5) Use a web-based EDC system to submit the DCF.

SITE REGULATORY AND PERFORMANCE REQUIREMENTS

Once regulatory requirements are met, training is completed, and the site agreement has been executed, the site will be activated for enrollment. All active sites are responsible for obtaining and maintaining IRB approval from their local or central IRB. In addition, sites are expected to follow Good Clinical Practice (GCP).

Failure to comply with the regulatory or performance requirements above will result in an internal review by [name] and the DCRI Study Team.

ETHICAL AND REGULATORY CONSIDERATIONS

RISK/BENEFIT ASSESSMENT OF QUALITATIVE INTERVIEW

There are no physical risks involved in this study. There is a very small risk that interview responses could inadvertently be disclosed outside the study in an identifiable way. We believe these risks to be minimal. As described in the next section, we will take several steps to protect the privacy of our participants and minimize any risks to confidentiality.

There is also a risk that some participants may feel uncomfortable answering questions regarding their ICD decision. To reduce this risk, the participant will be able to skip any interview questions they do not wish to answer and can stop participating at any time. Some participants may also seek interviewer input regarding the “right” decision. To minimize this risk, the interviewer’s introductory script will include information about his/her limited role and credentials (e.g., not a medical doctor or expert in the field, role only to understand how patients think through these topics).

This research is not expected to provide direct benefits to participants. However, by soliciting feedback about the ICD decision-making process, we hope our findings will better enable prospective recipients of ICDs to receive the information most helpful to informing their treatment decision.

PRIVACY, DATA STORAGE, & CONFIDENTIALITY

We will take many steps to maintain the privacy of our research participants and the confidentiality of the information they share. In particular, we will assign a code number to all interview materials. The only connection between the code number and direct identifiers will be a password-protected linkage file, stored at the Duke Clinical Research Institute (DCRI) and accessible only by study personnel. The linkage file will be kept separate from interview data, and will be destroyed upon completion of the project.

We will follow the data storage procedures described below, as well as assure compliance with the VIVID research data security plan regarding the iPads, iPad security and data transmissions:

- Paper study records will be stored in locked areas accessible only by the study team. Only key-card access is permitted within the DCRI. Secured waste receptacles are available on each floor for expired confidential printouts; this waste is shredded weekly.
- Electronic data will be stored on secure computers at the DCRI. The following describes DCRI data storage and security procedures, which are designed to maintain the confidentiality of research data. By restricting access to these confidential data, the

DCRI Network Infrastructure serves as the principal means of safeguarding this information from improper use or disclosure.

- The DCRI has extensive electronic data safeguard procedures in place. All data are securely stored on Unix servers (currently, Solaris 9 and 10 operating systems) that are behind the Duke Protected Health Information (PHI) firewall.
- At point of entry at the firewall, policy directs the denial or acceptance of certain types of Internet traffic from specific sponsors or sources. Connections to certain sites are also restricted. The router has access lists and commands to deny or permit traffic. Internal network software continually monitors the Intranet for the presence of viruses or worms and electronically quarantines any infected device.
- All users are required to have strong passwords, changed every 90 days, and not reused for 3 years. The system tools enforce the strong password provision at the time of password creation. Access to data is based on a person's role and need to know. All file and directory access is controlled by groups and users rights. Users must have the proper access rights to read, create, and modify files. All work areas are secured with electronic key access. Secure recycling is provided on each floor for sensitive paper disposal.
- The Unix servers are physically located in a secure IT server room with emergency power, non-liquid fire suppression, and authorization-based limited access. Server room access includes an audit trail.
- All users are authenticated, authorized, and accounted on the DCRI domain. Remote Access at the DCRI is granted one of two methods and only for DCRI authenticated individuals. The first method is a VPN (Virtual Private Network) connection (Firepass from F5). A VPN allows users to form an encrypted network connection via the Internet backbone. The Firepass VPN software checks the client's internal virus protection software and will not allow inadequately controlled clients to access the DCRI. The second method is Citrix access (Cisco Systems). Citrix clients use an ICA (Independent Computing Architecture) client. Once again, all connections are encrypted. Client and server data is secure while the connection is maintained. These technologies are in place at DCRI and are fully functional. Wireless (Wi-Fi) access to the DCRI is only available under the VPN or Citrix routes.

Reports, articles, and presentations of the study findings will include aggregate results only, and we will apply significant attention to ensuring that responses cannot be attributed to a particular panelist through direct or indirect inference.

ALTERNATIVES TO THE IPAD AND PROCEDURES

Patients who appear uncomfortable with the iPad consent process may, at the site's discretion, be offered supplemental consent discussions and support to ensure comprehension and agreement with participation. However, consent signature will still occur via the iPad so that data collection proceeds as outlined above. No alternative methods for consent or data collection will be available. Thus, patients who are not willing or able to sign the consent using the iPad will be unable to participate.

REFERENCES

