
OBJECTIVES

Using patient-centered racially distinct educational videos on SCD and ICD therapy, we will compare in black patients the effect of the video intervention vs. health care provider counseling (usual care) on 1) patient knowledge of SCD and ICD's, 2) the decision for ICD implantation and associated decisional conflict, and 3) ICD receipt within 90 days. We will also explore the influence of racial concordance between provider and patient video participants on the decision for ICD implantation, associated decisional conflict, and ICD receipt at 90 days.

Primary Outcome: 1. The decision for ICD implantation at 7 days among patients randomized to the video intervention compared with health care provider counseling (usual care) .

Additional Outcomes: 1. The effect of racial concordance on the decision for ICD implantation 2. Changes in patient knowledge (pre and post intervention). 3. Changes in decisional conflict (pre and post). 4. ICD receipt within 90 days of the decision for ICD implantation. 5. In-depth qualitative interviews of 90 patient participants that will focus on: a) knowledge of SCD and ICD therapy b) influences on the decision to accept or decline an ICD, c) impact of the video on the decision (critique of the video content) d) barriers to ICD placement following the initial decision. Lastly, study coordinators will assess the time spent with patients by providers in each arm of the study.

METHODS

ELIGIBILITY AND CONSENT

Inclusion criteria:

- 1) Non-hospitalized patients with ejection fraction $\leq 35\%$
- 2) New York Heart Association class I-III heart failure
- 3) Age > 21
- 4) Eligible for an implantable cardioverter defibrillator (ICD) for the primary prevention of sudden cardiac death
- 5) Self-identified race as black
- 6) Provision of informed consent to participate in the study.

Exclusion criteria:

- 1) Life expectancy < 12 months
- 2) Listed for Orthotropic Heart Transplantation (OHT)
- 3) Transplant (OHT) or OHT imminent within 12 months,
- 4) History of ventricular fibrillation or sustained ventricular tachycardia without reversible causes
- 5) ICD already implanted
- 6) Myocardial infarction within the last 40 days
- 7) Coronary revascularization within the last 3 months
- 8) Patients who are unable to understand the study procedures due to cognitive or language barriers

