- 9) Inpatients will be excluded from the study because decision-making processes are thought to be appreciably different in inpatients as compared with outpatients.
- 10) Plan for subcutaneous ICD (Sub-Q ICD)

[figure not shown]
SCREENING, ENROLLMENT, AND CONSENT PROCESS

Figure 1: Study Processes

Study processes are outlined in Fig. 1. Patients will be screened for participation/eligibility by the Research Assistant (RA), prior to the patients scheduled visit to the electrophysiology clinic. An introductory letter will be sent to potential patients by mail from their provider and research team. At the electrophysiology clinic visit, the RA will approach the patient about participation in the project. At that time (baseline visit), the RA will review

study procedures and begin the consenting process. The consent process will include a full explanation of the research protocol and aims, as well as use of the iPad technology for the patient to review and sign the consent. The patient will also review and sign a medical release form, to facilitate patient follow-up, if the patient is not available via phone. In certain U.S. states, the patient will also review and sign a bill of rights statement. Following the consent and other document(s) signature process, the patient will provide baseline demographics (age, gender, payer status, household income, education, distance from health care facility, method of transportation, current employment status and a number of other social determinants), followed by administration of the Health Related Quality of Life Survey (HRQOL) SF-12v2, a depression assessment PHQ- 2, knowledge questionnaire and the decisional conflict scale (DCS), on the iPad. The patient will then be randomized on the iPad to one of three study arms (see below). The patient will view a video (per randomization) or consult with their provider to discuss the ICD procedure. After exposure to their assigned arm (video or usual care), patients will be administered the same knowledge questionnaire on the iPad, prior to the conclusion of the visit. Using the iPad at the end of the visit, the RA will note the length of time the patient spent with the provider.

Figure 1

BASELINE VISIT DATA

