Following consent and other processes on the iPad, the RA will collect baseline visit data from the patient's medical record, including medical history, heart failure classification (NYHA), etc. The baseline data will be entered into the Data Collection Form (DCF). The DCF is an electronic web-based form in the Registry System, used at the DCRI for data collection.

RANDOMIZATION AND BLINDING

Participants enrolled in the study will be randomized on the iPad to 1 of 3 arms, A) video with black participants, B) video with white participants, or C) usual care (UC): health care provider counseling (Figure 2). For the outcomes not based on racial concordance, patients in ARM A and ARM B (video arms) will be combined and compared with UC. Study participants will be blinded to differences in the 2 videos.

Arm A: white video

Arm B: black video

Arm C: Health care provider consult only (usual care)

Figure 2: Form and Content of Information Conveyed in 3 Study Arms

	Arm A	Arm B	Arm C
	White ICD Educational Video	Black ICD Educational Video	Usual Care
Video featuring predominantly Black patients & health care professionals		X	
Video featuring predominantly White patients & health care professionals	X		
Chapter 1: Introduction	X	X	
Chapter 2: SCA and the heart's electrical system	X	X	
Chapter 3: Are you at risk? The importance of ejection fraction	X	X	
Chapter 4: Therapies to prevent SCA and ICDs	X	X	
Chapter 5: Making the right decision for you – a patient's perspective	X	X	
Chapter 6: Living with an ICD	X	X	
Health provider driven discussion (standard of care)			X

DATA SUBMISSION AND SITE TRAINING

For each patient enrolled, the RA will be responsible for submitting the iPad data and entering the baseline visit data via the DCF within a short period of time. Data submission for both the iPad and DCF will be essential to facilitate patient follow-up. All sites will be trained on the VIVID Protocol, use of the iPad and Registry System, and the site materials. The DCRI study team will ship all site materials, including the iPad, and provide the site team with access to the Registry System.

POST-INTERVENTION VISIT ACTIVITIES

Outcomes Call Center (OCC)

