Sampling	
Up to 90 IDIs, stratified by initial ICD decision:
 
 • 30 Acceptors • 30 Refusers • 30 Unsure 
Within each group, patients will be purposively samples to ensure we speak to a diverse range of participants (e.g., based on region, gender, education level, etc.)
	
Up to 60 follow-up IDIs, to be completed with a sub-set of patients. Follow-up interviews will be completed with three groups of patients (with their consent):
 
 • Patients who were originally unsure about ICD implantation • Discordant Cases 
 - Patients who originally accepted ICD but had not had it implanted at -day follow-up - Patients who originally rejected ICD but had it implanted at 90-day follow-up
Interview Time Points	Consenting patients will be contacted within a few days of their 1-week follow-up to schedule a time to complete the IDI	Consenting patients will be contacted within a few days of their 90-day follow-up to schedule a time to complete the IDI
Content	
 - Examine thoughts and opinions regarding educational component (health care provider counseling, video only) - Explore considerations important to ICD decision-making process - Interview Guide, for use by the DCRI Team 	
 - For patients originally unsure about an ICD, better understand processes/considerations that ultimately led them to accept or refuse the ICD - For discordant cases, examine factors that led to shift in initial acceptance/refusal decision.
Duration	Between 60-90 minutes	Between 30-45 minutes
Compensation	Patients will be compensated \$50 for their time.	Patients will be compensated \$25 for their time
Consent	The original consent form includes a description of IDI opportunities. At one-week/90-day telephone call, the interviewer will ask the participant if he/she is interested in completing an IDI (see In-Depth Script Language). Interested patients who also meet inclusion criteria may then be contacted by the IDI	

	interviewer, who will further describe the interview and answer patient questions (see Information Sheet, which interviewer will discuss by phone and send to participant by email or traditional mail). Telephone interviews will be scheduled for participants who wish to complete the interview.
--	--

INTERVENTIONS

BLACK INDIVIDUAL FOCUSED ICD EDUCATIONAL VIDEO

(25 minutes):

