The patients and health care professionals in the video will be predominantly black. This video will be available on the iPad, if the patient is randomized to watch this video. For site training, the video is available on YouTube. Enter “ICD YouTube” into web browser. Click on the ICD – YouTube link that states: African American by Duke Clinical Research Institute. Additionally, we have both videos in DVD format if preferred by sites.

Chapter 1 Introduction

Chapter 2 Sudden cardiac arrest (SCA) and the heart’s electrical system.

Indicates normal components of electrical system (SA node, AV node, is bundle)

Discusses ventricular arrhythmias

Chapter 3 Are you at risk? The importance of ejection fraction (EF)

Discusses the association between EF and SCA. Ejection fraction as a measure of heart function

Chapter 4 Therapies to prevent SCA and implantable cardioverter defibrillators (ICDs)

The efficacy of medical therapy (b-blockers and ace inhibitors in prevention of SCA in patients with left ventricular dysfunction. Describes the ICD and how it works and the implantation procedure and potential complications

Chapter 5 Making the right decision for you: a patient’s perspective

Patients will discuss their decision-making process regarding ICD placement.

Chapter 6 Living with an ICD

Patient testimonial about what a shock feels like. How is life different with an ICD.

Details about remote monitoring and device follow up.

The video will consist of patient testimonials, educational segments with visual animation, physician commentary, and narration.

WHITE INDIVIDUAL FOCUSED ICD EDUCATIONAL VIDEO

(25 minutes):

Same content as above with predominantly white participants. This video will be available on the iPad, if the patient is randomized to watch this video. For site training, the video is available on YouTube. Enter “ICD YouTube” into web browser. Click on the ICD – YouTube link that states: Caucasian by Duke Clinical Research Institute. Additionally, we have both videos in DVD format if preferred by sites.

USUAL CARE

Health provider driven discussion, which is the predominant counseling mode utilized at participating sites.

STUDY INSTRUMENTS

KNOWLEDGE QUESTIONNAIRE

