Since there is no existing decisional conflict scale (DCS) for assessing decisional conflict associated with ICD implantation, we have modified a previously validated DCS used for decision-making in breast cancer screening, influenza vaccination, and coronary revascularization procedures. This tool was also developed with the assistance of our patient, provider and general public focus groups and our stakeholder advisory panel. This DCS was tested in our pilot study and performed well. The DCS will measure the effect of the video on decisional conflict and the decision for ICD placement. The overarching goals of the DCS are to assess overall decisional conflict measured through five subscales: 1) informed subscale 2) values clarity subscale, 3) support subscale, 4) uncertainty subscale and 5) effective decision subscale. Prior to the intervention and at 1-week post intervention, participants will be asked to give their decision for ICD implantation (yes, no, unsure) followed by the administration of the DCS. Respondents will be asked to reflect on their decision and respond to the DCS questions using a 5-point Likert scale. Responses to each statement are scored 0 (strongly agree) to 4 (strongly disagree). Total scores range from 0 to 100, with higher scores indicating greater decisional conflict (Appendix B). We will compare the delta change pre to post DCS scores across study arms. To determine the effect of racial concordance between video participants (physicians and patients with ICD's and their families in the video) and study participants we will compare the delta change in pre and post DCS scores, decision for ICD implantation, and ICD receipt within 90 days of the decision in racially concordant intervention compared with racially discordant intervention.

IN-DEPTH INTERVIEW GUIDE

The Round 1 in-depth Interview Guide is designed to elicit patient perspectives on the educational information they received regarding the ICD, including information that was reassuring, concerning, confusing, etc. Patients randomized to a video arm will be asked specific questions about the video component. All patients will be asked questions regarding the conversation they had with their provider. In addition, patients will be asked a series of questions to better understand factors and individuals important to their ICD decision. The guide

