1.4 Study Design

Study processes are outlined in Fig. 1.

The Research Assistant (RA) will screen patients for participation/eligibility, prior to the patients scheduled visit to the electrophysiology clinic. When possible an introductory letter will be sent to potential patients by mail from their provider and research team. At the electrophysiology clinic visit, the RA will approach the patient about participation in the study. At that time (baseline visit), the RA will review study procedures and begin the consenting process. The consent process will include a full explanation of the research protocol and aims, as well as use of the iPad technology for the patient to review and sign the consent. The patient will also review and sign a medical release form, to facilitate patient follow-up, if the patient is not

available via phone. In certain U.S. states, the patient will also review and sign a bill of rights statement. Following the consent and other document(s) signature process, the patient will provide baseline demographics (age, gender, payer status, household income, education, distance from health care facility, method of transportation, current employment status and a number of other social determinants), followed by administration of the Health Related Quality of Life Survey (HRQOL) SF-12v2, a depression assessment PHQ- 2, knowledge questionnaire and the decisional conflict scale (DCS), on the iPad. The patient will then be randomized on the iPad to one of the three study arms: A) video with black participants, B) video with white participants, or C) usual care (UC), i.e. clinician counseling. The patient will view a video (per randomization) or consult with their clinician to discuss the ICD procedure. After exposure to their assigned arm (video or usual care), but prior to the conclusion of the visit, patients will be administered on the iPad the same knowledge questionnaire as before the randomization. Using the iPad at the end of the visit, the RA will note the length of time the patient spent with the provider using an iPAD based timer.

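### Is it left undefined whether the trial tests a video in place of provider counselling or on top of it?

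*Protocol*

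**What the plan says.** Several places describe the assigned exposure as one thing or the other:

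- Protocol, Screening, Enrollment, and Consent Process: "The patient will view a video (per randomization) or consult with their provider to discuss the ICD procedure".
- SAP 1.4: "The patient will view a video (per randomization) or consult with their clinician to discuss the ICD procedure".
- Protocol Figure 2 has a row "Health provider driven discussion (standard of care", marked for Arm C and blank for the two video arms.
- Protocol, Interventions, defines usual care as "Health provider driven discussion, which is the predominant counseling mode utilized at participating sites".
- Protocol Figure 4 lists the educational components for the interviews as "health care provider counseling, video only".

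Other places take provider contact in the video arms for granted, or could be read that way:

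- Protocol, In-Depth Interview Guide: "All patients will be asked questions regarding the conversation they had with their provider".
- Protocol, Objectives: "study coordinators will assess the time spent with patients by providers in each arm of the study". SAP 1.2 and 2.3.6 make this a secondary comparison, including between the two video arms.
- Protocol, Randomization and Blinding: "Arm C: Health care provider consult only (usual care".

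The primary comparison itself is fixed. The Protocol's Analysis Plan and SAP 2.2 compare both video arms combined with usual care on ICD acceptance at 7 days, by a Pearson chi-square test.

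**The concern.** Figure 2 sets out what information each arm conveys, and its blank cells suggest that video patients have no provider-led ICD discussion. The interview guide suggests that they do have a conversation with the provider. A video that replaces counselling and a video that supplements it are different strategies with different consequences for practice. The chi-square test is identical for both, so a positive result would not by itself show which strategy had been tested. The provider-time comparison would also change meaning: it would describe either a visit from which ICD counselling was removed, or counselling that followed a video.

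**Working it through.** **What each place is for.** The weight of a sentence depends on whether it defines treatment.

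| Place | Function | Contrast or content |
|---|---|---|
| Protocol, Objectives and primary outcome | defines the comparison | video against provider counselling |
| Protocol, Screening, Enrollment, and Consent Process; SAP 1.4 | visit procedure | video or consult |
| Protocol, arm list and Figure 2 | arm content | provider discussion marked for Arm C |
| Protocol, Interventions | arm content | two videos and usual care, listed separately |
| Protocol, Analysis Plan; SAP 1.1 | defines the comparison | video against standard of care or clinician counselling |
| Protocol, In-Depth Interview Guide | content of a later telephone interview | all interviewees asked about a provider conversation |
| Protocol, Objectives (time); SAP 1.2 and 2.3.6 | measurement | minutes with the provider, every arm |

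The first five rows agree. The sixth is the only sentence that pulls clearly the other way. It concerns up to 90 selected interviewees, contacted after their 1-week follow-up, with a guide that Figure 4 reserves for the coordinating centre's team. It tells no site what to deliver.

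**Whether the passages can coexist.** Patients are approached at an electrophysiology appointment already scheduled, so they can be expected to see a provider whatever their arm. If the video or the counselling is read as the assigned educational exposure, with ordinary clinic contact around it, all the rows fit:

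- Figure 2 then tabulates the assigned component.
- The timer records minutes with the provider, not minutes of ICD counselling.
- The word only in the Arm C label may simply mean that no video is shown.

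Both documents refer to Figure 1 for the study processes, and the interview guide is Appendix C. Neither is available here, and either may give the order of events.

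**Whether any number depends on the answer.** The inputs from SAP 1.5 are 103 usual care and 206 video patients (309 in all), usual-care acceptance 43%, and type I error 0.05, taken as two-sided. With p1 the usual-care rate, p2 the video rate and d = p2 − p1:

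- pooled rate p = (103·p1 + 206·p2)/309
- SE0 = √[p(1−p)(1/103 + 1/206)]
- SE1 = √[p1(1−p1)/103 + p2(1−p2)/206]
- power = Φ[(d − 1.96·SE0)/SE1]

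For 43% against 63%: p = 0.5633, SE0 = 0.0599, SE1 = 0.0593, and power = Φ(1.395) = 91.9% (stated 91%).

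For 43% against 60%: p = 0.5433, SE0 = 0.0601, SE1 = 0.0595, and power = Φ(0.876) = 81.0% (stated 80%).

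Both figures reproduce to within about one point, and no input describes provider contact. Power does depend on the true difference. With assumed differences of 15, 10 and 5 points the same formula gives 70%, 38% and 13%. The documents give no separate effect for either reading, so none of these values can be attached to one of them.

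**Whether any analysis changes.** Patients are compared by randomised arm, so the chi-square test keeps its validity whatever contact accompanied the video. The second knowledge questionnaire is tied to the assigned exposure (Protocol, Knowledge Questionnaire; SAP 2.3.2) and the decision to 7 days. Neither time moves.

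**The case for a change.** The strongest opposing case rests on two points. Figure 2's title says that it shows the information conveyed in each arm, so blank cells should mean that the provider conveys none. The interview guide is about ICD information received, and its question on the provider conversation follows one on the video, so the natural reading is an ICD discussion in every arm. On that view the two do not fit, and some sites might apply Figure 2 literally while others hold their routine discussion with everyone. SAP 2.2 also examines whether the effect differed before and after the shared-decision regulations, which is harder to read if the content of the video arms is uncertain. The timer records duration, not content.

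Part of this stands. The available text does not say outright whether video patients also discuss the ICD with the provider at the visit, and the answer affects how the 7-day difference, the provider-time result and the before-and-after comparison are described.

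The rest does not. The contrast is stated, consistently, wherever treatment is defined. Sites would not vary their delivery because of an interview guide that they do not use. If delivery did vary, the result would still be the randomised effect of assignment to a video at such a visit. Nor does it measure impact that the video arms hold 206 of 309 patients (67%): that is only two arms pooled against one.

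**Conclusion.** No change to the plan is needed. There is a real tension in wording between Figure 2, with the either-or phrasing in both documents, and the interview guide. It is a missing detail rather than a rule that yields a wrong result. No test, assessment time, sample size or power figure changes, and any effect on the estimate cannot be computed from the documents.

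This rests on two assumptions: that the interview guide does not govern what sites deliver, and that some provider contact at a scheduled electrophysiology visit is ordinary. Figure 1 and Appendix C could confirm or refine the picture. If they leave the passages at odds, the trial team can reconcile them in one sentence and describe the primary contrast and the SAP 2.3.6 result to match. Nothing here says which arm content is right.
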